### ***Research Question***

More specifically, the following research question needs to be addressed :

Can sEMG parameters predict upper extremity motor function recovery in acute stroke patients?

### ***Study Objective***

The aim of the study are:

To know if sEMG parameters can predict upper extremity motor function recovery in acute stroke patients

### ***Study Benefits***

This study has numerous benefits, it can help us gain a better understanding of complex issues, develop new technique, determine discharge planning, improve outcome of rehabilitation program, and inform public policy.

The results of this study are expected to enrich our knowledge and become a base for future research. The results of this study are also expected to be an aid in determine prognostication to promote functional outcomes in stroke patients.

## LITERATURE REVIEW

### Upper Extremity Motor Impairment Post Stroke

Upper extremity weakness is the most common impairment of stroke patients, which plays an important role in motor function deficiency and has a detrimental effect on the quality of life.

Upper extremity impairments after stroke are the cause of activity limitations, participation restrictions, and reduced independence in daily life with regard to use of the affected upper extremity after stroke, so a clear understanding of the underlying impairments is necessary to provide appropriate treatment. Understanding upper extremity impairments in any given patient is complex for two reasons:

- 1) The impairments are not static, for example as motor recovery proceeds, the type and nature of the impairments may change, therefore the treatment needs to evolve to target the impairment contributing to dysfunction at a given point in time.
- 2) Multiple impairments may be present simultaneously, for example a patient may present with weakness of the arm and hand immediately after a stroke, which may not have resolved when spasticity sets in a few weeks or months later, hence there may be a layering of impairments over time making it difficult to decide what to treat first.

It is useful to review the progression of motor recovery as described by Twitchell and Brunnstrom to understand how impairments may be layered over time (Figure 1).

[figure not shown]

Figure 1. Sequential progression of motor recovery. Quoted from: Raghavan P. Upper Limb Motor Impairment After Stroke. *Phys Med Rehabil Clin N Am.* 2015;26(4):599-610

Prabhakaran et al. proposed a proportional recovery rule. According to this rule, the majority of stroke survivors are expected to recover approximately 70% of their maximum potentials at 3 months after a stroke.

A rule of thumb in stroke recovery is that patients with mild deficits are more likely to make a good recovery than patients with initially more severe deficits (Figure 2). The most significant improvements occur in the first few weeks post-stroke, often reaching a relative plateau after 3 months with less significant recovery subsequently. After 6 months, spontaneous recovery is usually at its limit, leading to a more or less stable, for example, chronic deficit.

[figure not shown]

Figure 2. Motor recovery after stroke in a sample of  $n = 412$  ischemic stroke patients based on the Fugl-Meyer upper extremity (FM-UE) score. Quoted from: Grefkes C, Fink GR. Recovery from stroke: current concepts and future perspectives. Neurol Res Pract.2020;2:17

Recent studies confirmed that the patient clinical features assessed at the baseline, predicted the final outcomes of the motor treatment. Some of the following features have positive predictive value on upper extremity prognosis after stroke, and one of them is the presence of any muscle contraction when attempting to perform a movement.

Ability to volitionally perform a movement of in individual's suffering stroke usually done through manual muscle testing (MMT). Manual muscle testing

is recommended for initial assessments because it is quick and provides standardized measures of motor function.

MMT is performed with the hands of the therapist or physician. MMT use a five-point scale defined as normal, good, fair, poor, trace and zero, and assesses muscles that perform a joint motion, rather than individual muscles as described in Table 1. The required assessment time is shorter, and at the same time, important information is provided about the patient's muscle strength. Some MMT can be performed in the supine position.

Table 1. Manual Muscle Testing Scoring System.

Grade	(%)	Qualitative value	Muscle strength
5	100	Normal	Complete range of motion (ROM) against gravity, with full resistance
4	75	Good	Complete ROM against gravity, with some resistance
3	50	Fair	Complete ROM against gravity, with no resistance
2	25	Poor	Complete ROM with a gravity omitted
1	10	Trace	Evidence of slight contractility, with no joint motion
0	0	Zero	No evidence of muscle contractility

Quoted from : Brown M, Hislop H, Avers D. Daniels and Worthingham's muscle Testing-E-Book: Techniques of manual examination and performance testing: Elsevier Health Sciences; 2013

Currently, besides MMT, patients with upper extremity motor impairment also assessed mainly by clinical scales, with the Fugl-Meyer test being one of the most commonly used measures of motor impairment after stroke to provide a more detailed description of the patient's clinical condition. The functional diagnosis

allows the medical practitioners to set the post-stroke patients' rehabilitation objectives, and can also provide a perspective on the future rehabilitation potential and prognosis, and on the necessary timeframe.

Fugl-Meyer Assessment (FMA) is the first stroke-specific assessment tool that was developed on the basis of Brunnstrom's motor recovery stages. It is a feasible, well-designed, responsive, and efficient tool. The FMA is considered by many in the field of stroke rehabilitation to be one of the most comprehensive quantitative measures of motor impairment following stroke, and its use has been recommended for clinical trials of stroke rehabilitation.

The FMA is based on the natural progression in post-stroke hemiparesis. The upper extremity subsection of FMA (FMA-UE) is commonly used as compared with other parts in post-stroke patients. The FMA-UE comprises 33 items related to the movements of proximal and distal upper extremity. The maximum motor performance score is 66 points for upper extremity. Scoring is done on a 3-point ordinal scale ranging from 0 (item cannot be performed) to 2 (items can be performed faultlessly) by the direct observation of the movement performance. The FMA-UE requires 10-20 min for its administration.

The FMA-UE assesses the post-stroke subjects as per the sequential recovery stages. The items are hierarchically organized from synergistic to voluntary movements. Synergistic movement exhibits an abnormal stereotyped behaviour that does not allow the combination of different movement patterns, for example, an attempt to raise the arm results in elbow flexion, shoulder abduction and internal rotation. The components of flexor and extensor synergy are tested

before the movements combining synergies and out of synergy. Each item of FMA-UE subsection, further, has multiple components that allow an examination of the wide and complex motor changes.

### **Surface Electromyography**

Electromyography (EMG) is the recording of the electrical activity of muscles, and therefore constitutes an extension of the physical exploration and testing of the integrity of the motor system. It can be said that surface electromyography (sEMG), sometimes called kinesiological electromyography, is the electromyographical analysis that makes it possible to obtain an electrical signal from a muscle in a moving body.

Surface EMG's is only requiring adequate electrode contact with the skin to function. This sensing capability does not require sophisticated hardware and can be made either in a benchtop or portable scale. It does not require dedicated personnel to operate, and can be constructed cost-effectively for a variety of applications.

When the brain instructs the body to move, it sends an electrical impulse signal down the spinal cord and through an intricate network of peripheral nerves to the targeted muscle. This neuronal signal is transduced into a muscular contraction by numerous neurons known as motor units, each consisting of a motor neuron (anterior horn cell), its axon, and all the individual muscle fibres it innervates (Figure 3). Upon arrival of the electrical impulse from the brain, the motor units quickly depolarize the cell membrane space of their respective axon

terminals, leading to a propagating action potential wave that travels across the muscle fibres. Since an activation impulse from the brain can recruit multiple motor units, all the resultant motor unit action potentials (MUAPs) become superposed as their electrical signals radiate through the muscle. The resultant electrical signal can be sensed on the skin by the surface of electrodes, giving the characteristics EMG signal. Smaller muscle motions with fewer recruited motor units therefore exhibit low amplitude EMG signals, while large muscle motions conversely result in high amplitude EMG signals.

[figure not shown]

Figure 3. A single motor unit and the muscle fibers it innervates. Quotes from: Zheng M, Crouch MS, Eggleston MS. Surface Electromyography as a Natural Human–Machine Interface: A Review. *IEEE Sensors Journal*. 2022;22(10):9198–9214.

Steele et al. study showed that among 21 patients they were monitored, muscle contractions were detected from all five muscles (deltoid, biceps, triceps, wrist flexors, and wrist extensors) during a single four hours collection period

during standard care even for the 11 patients who had an MMT score of zero, indicating no voluntary movement or muscle activity detected via palpation. In the patients who were initially flaccid, they did find moderate correlations between early contraction characteristics and scores on the MMT at follow-up. These findings indicate that muscle activity is present during the first week after stroke, even among participants characterized as flaccid, and EMG can provide quantitative metrics that may have prognostic value for predicting future function.

The use of sEMG involves three phases (the preparation phase, the recording phase and the processing phase) which are described below:

1. Preparation phase

a) Preparation of the individual and the provision of information in advance.

It is essential to adequately inform the individual about the procedure to be followed during the recording session and about particular aspects of the study, such as its objectives, usefulness and possible applications. It is necessary to obtain the individual's informed consent in writing.

b) Preparing the skin.

The skin's impedance must be reduced so as to obtain a good quality electrical signal. It is advisable to shave and rub the skin with an abrasive gel to reduce the dry layer of the skin or dead cells, and to eliminate sweat by cleaning the skin with alcohol.

c) Positioning the electrodes

It is essential to position the electrodes correctly to obtain a good signal.

The best position, provided it is possible, is on the mid line of the muscle

belly, between the myotendinous junction and the motor point. The published guides like Surface Electromyography for the Noninvasive Assessment of Muscles (SENIAM) guidelines can be used to ensure the methodology is followed correctly. It is very important to always use the same position on different individuals and for different recordings taken from the same individual, given that the signal recorded varies according to the area of the muscle on which the electrodes are positioned. It is also advisable to maintain an optimum distance between the electrodes. Each muscle is examined by positioning two electrodes on it, separated by a distance of one or two centimetres.

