Individuals with no volitional movement, however, the FMA-UE or MMT alone cannot determine whether muscle activity is present. MMT score of 0 can indicate severe paresis with no muscle activity, that the muscle activity is below the level necessary to produce observable contractions, or that the patient was unable to fully participate in the assessment. Patients with an MMT of 0, this can be frustrating as the patient and their clinical team take a “wait-and-see” approach to determine whether muscle activity will return.

Ongoing research continues to explore areas of brain plasticity, neural recovery mechanisms, and prognostication of stroke outcomes to maximize

recovery, while there has been simultaneous advancement in wearable sensor-based technologies that provide additional, non-invasive means of examining neuromuscular pathways and recovery processes following stroke.

One of these wearable sensor-based technologies is surface electromyography (sEMG). Surface electromyography (sEMG) provides a non-invasive window into the nervous system that can be used to monitor muscle activity, but is rarely used in acute care. Steele et al have demonstrated that deploying sEMG in acute care is both feasible and useful. They found that current technology can be used to comfortably and non-obtrusively monitor muscle activity, even for patients with no detectable muscle activity by traditional clinical assessments. They perceive opportunities in using sEMG to inform prognosis, enable biofeedback training, and provide metrics necessary for supporting and justifying care for further research.

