Stinear et al combined clinical predictors and corticospinal tract biomarkers to predict 1 of 4 upper limb functional outcome categories at 3 months poststroke. The Predict Recovery Potential (PREP) algorithm was developed in a study of 40 participants and externally validated in a subsequent study of 157 participants. The PREP2 algorithm begins with the Shoulder Abduction, Finger Extension score (SAFE) determined within 72 hours of stroke. Each of these movements made with the paretic upper limb is evaluated with manual muscle testing and scored out of 5 with the Medical Research Council grades. The scores are summed to determine the SAFE score, and if the score is at least 5 out of 10, the patient's age is all that is required to predict either an Excellent or Good upper limb outcome, but if the SAFE score is <5 out of 10, then transcranial magnetic stimulation is needed to test the function of the corticomotor system. A good outcome is predicted if motor-evoked potentials can be elicited in the paretic upper limb. The NIHSS score is used to predict either a limited or poor upper limb outcome if motor-evoked potentials cannot be elicited. The PREP2 algorithm is accurate for 75% of patients, and using it in clinical practice increases therapist confidence, allows tailoring of upper limb therapy, and is associated with a reduced length of stay. A recent follow-up study found that PREP2 predictions remained accurate for most patients at 2 years poststroke. A major limitation of PREP2 is that transcranial magnetic stimulation is not readily available in many clinical settings.

Adopting wearable sensors like sEMG in acute care will ultimately require that these sensors provide unique and valuable insights that are not available with current methods. Beyond detecting muscle activity, longitudinal evaluations will determine the diagnostic and prognostic value of sEMG in acute care.

Christina Papazian et al. study found that monitoring muscle activity with dual mode sensors of sEMG during acute care could detect contractions in the major arm muscles of stroke survivors, even among those who had no observable activity from clinical examination. In their exploratory analyses, they found modest correlations between contraction characteristics and future function for the participants with an MMT of 0.

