### **Study participants**

Potential participants will be recruited by the main researcher

Inclusion criteria:

1. Patients who are hospitalized with upper extremity weakness due to stroke on the same side which confirmed with computed tomography (CT) scan or structural magnetic resonance imaging (MRI), in the acute phase
2. Men and women aged more than 18 years old
3. Willing to participate

Exclusion criteria:

1. Cognitive impairment (MoCA-Ina score less than 26)
2. Impaired consciousness (GCS score less than 15)
3. Unstable medical conditions at time of hospitalization
4. Patients with pacemaker

5. Having other injury or dysfunction in the impaired side of upper extremity that caused restrictions on the range of joint movement and muscle weakness, such as fractures, periarthritis, or moderate-severe pain
6. Diagnosis of other neurological disease or disorders in addition to stroke (e.g., traumatic brain injury, neuropathy or radiculopathy)
7. Get treated in isolation room
8. Hypersensitivity to gel electrodes

Drop out criteria:

1. Unable to do 2 or more follow up session
2. Withdrawn by themselves

Confounding factor:

1. Stroke location
2. Stroke size
3. Spasticity
4. Rehabilitation program
5. Compliance rehabilitation
6. Stroke risk factor

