## Sample Size Determination

Samples are taken from research subjects that meet the inclusion criteria.

The sample size to test the pair averages then the large determination of the sample, carried out on the basis of statistical calculations by setting the 95% confidence level of the two-way hypothesis and the power test 95%.

Sample determination for categorical numerical analytical research pairs using the formula:

$$n_1 = n_2 = \left( \frac{(Z_\alpha + Z_\beta)S}{X_1 - X_2} \right)^2$$

Where:

$Z_\alpha$  = alpha standard deviation

$Z_\beta$  = beta standard deviation

$S$  = combined standard deviation.

$X_1 - X_2$  = average minimal difference that is considered significant

Type I error is determined as 5%, hence two-ways hypothesis  $Z\alpha = 1,96$

Type 2 error determined as 5%, hence  $Z\beta = 1,64$

Based on the formula, the value is entered into the sample size formula as follows:

$$n_1 = n_2 = \left( \frac{(Z_\alpha + Z_\beta)S}{X_1 - X_2} \right)^2$$

$$n_1 = n_2 = \left( \frac{(1,96 + 1,64) * 1}{1} \right)^2$$

$$= 12,96 \approx 13$$

The minimum sample size for the pre-post test group is 13 people. The minimum number of samples required is 13 samples. The minimum sample number is added to the 10% possibility of sample exclusion so that the minimum sample size is  $13 + 1.3 = 14.3 \approx 15$  samples.

According to Gay and Diehl (1992), the sample must be as large as possible. This opinion assumes that the more samples taken, the more representative they will be and the results can be generalized. The sample size depends on the type of research:

1. The research is descriptive, so the minimum sample = 10% of the population
2. Correlational research, minimum sample is 30 units
3. Comparative causal research, the sample is 30 units per group
4. Experimental research, the minimum sample is 15 units per group

Based on the opinion of Gay and Diehl (1992), the minimum sample for this study for comparative analysis is 30 people. Based on the formula above, the minimum sample size for this research is adequate, so the minimum sample size is 30 samples.

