## Dummy Table

Table 2. Dummy Table

Variable	In Hospital				Follow Up			Difference in change at 3 months
	3 days	Discharge	P-Value	1 Months	2 Months	3 Months	P-Value	
MMT score								
FMA-UE score								
Contraction								
Length of contraction								
Amplitude								

Note: For numerical data, the p value is tested using the paired T test if the data is normally distributed and the alternative Wilcoxon test if the data is not normally distributed. Then, to compare numerical variables between pairs of more than two groups using the repeated ANOVA test if the data is normally distributed and the alternative Fredman test. The significance value is based on a p value of <0.05. The \* sign indicates a p value <0.05, meaning it is significant or statistically significant.

Table 3. Characteristic Table

Variables	p-Value
Sex	
Women	
Men	
Age	
Length of stay	
Stroke diagnosis	
Ischemic stroke	
Haemorrhagic stroke	
Stroke side	
Right hemisphere	
Left hemisphere	
Dominant Hand	
Right	
Left	
Stroke severity	
Minor stroke	
Moderate stroke	
Moderate to severe stroke	
Severe stroke	
Stroke risk factor	
Hypertension	
Diabetes Mellitus	
Heart disease	
Dyslipidemia	
Smoking	
Recurrent stroke	
Yes	
No	

Note: categorical data is presented in number, frequency, and percentage, while numerical data is presented in mean, median, standard deviation, and range.

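### The plan pools MMT 0 patients with all other arm weakness and tests only change over time, so it cannot show whether early sEMG predicts recovery; a pooled correlation added later could reflect initial severity alone

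*Combined protocol and SAP*

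**What the plan says.** All references are to the combined protocol and SAP.

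- **Rationale.** Study Background says that in people with no volitional movement "the FMA-UE or MMT alone cannot determine whether muscle activity is present". Two sEMG findings on later function are reported. Problem Statement says of one study that "they found modest correlations between contraction characteristics and future function for the participants with an MMT of 0". The Surface Electromyography section says of another: "In the patients who were initially flaccid, they did find moderate correlations between early contraction characteristics and scores on the MMT at follow-up". Premises 4 and 5 also concern flaccid or MMT 0 patients.
- **Target.** The Research Question, Study Objective and H1 are worded for acute stroke or stroke patients in general.
- **Eligibility.** The first inclusion criterion reads "Patients who are hospitalized with upper extremity weakness due to stroke on the same side", confirmed by imaging in the acute phase. No MMT limit or stratum is set.
- **Recording.** In Research Work Procedure, step 7i, subjects carry out five movements over 30 minutes; for those with MMT 0 the researcher performs passive range of motion.
- **Analysis.** Data Analysis lists paired t or Wilcoxon tests, repeated-measures ANOVA or Friedman tests, and McNemar or marginal homogeneity tests. Table 2 has one row per measure for the whole sample, five visits, and a final column "Difference in change at 3 months". MMT appears under Study Variable only as a dependent variable, and the list of confounding factors omits initial arm strength.

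**The concern.** Two things are missing between the question and the planned results.

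First, prediction is a relation across patients between an early measurement and a later outcome. The plan only asks whether averages change between visits. Most patients are expected to improve in the first three months, so a significant time trend is likely whether or not day-3 sEMG carries prognostic information.

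Second, the obvious repair, a correlation over all patients, would mix two groups that the protocol itself expects to differ. The Surface Electromyography section says that fewer recruited motor units give lower amplitude. The Literature Review says that milder initial deficits recover better. The recording condition differs as well. A pooled association could therefore restate how weak the arm was on day 3, which the bedside examination already shows. At stake is a claim that sEMG informs prognosis where examination cannot, resting on a result that does not separate one MMT 0 patient from another.

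**Working it through.** **1. The plan's own sample size.** Sample Size Determination sets "Type I error is determined as 5%, hence two-ways hypothesis" 1.96, and "Type 2 error determined as 5%, hence" 1.64, with S = 1 and a minimal difference of 1.

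- n = ((1.96 + 1.64) × 1 / 1)² = 12.96, so 13.
- 13 + 1.3 = 14.3, so 15.

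These reproduce. The final 30 comes from a cited rule of thumb. The formula is for a paired pre-post mean. It addresses neither a correlation nor an MMT subgroup.

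**2. Do the planned tests bear on prediction?** Simulate 30 patients with a mean change of 1 SD (the plan's own standardised effect) and a baseline sEMG value unrelated to that change. The paired t test is significant in 99.96% of runs, while the mean correlation between baseline sEMG and change is 0.00. A positive planned test is fully compatible with no prediction.

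**3. What a pooled correlation would do.** Inputs:

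- N = 30 (Sample Size Determination), two-sided 5% level.
- MMT 0 share: not given for this study, so assumed. The upper value follows the cited study, 11 of 21 (52%), about 16 of 30. The lower value is 20%, 6 of 30. The MoCA-Ina and GCS exclusions may reduce the share.
- Gap d between MMT 0 and MMT ≥1, in within-group SDs, taken as equal for day-3 sEMG and 3-month FMA-UE: assumed, 1 to 2.
- Correlation inside each group: set to zero.

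With p the MMT 0 share, the pooled correlation is r = p(1−p)d² / (1 + p(1−p)d²). Example: p = 0.2, d = 2 gives 0.2 × 0.8 × 4 = 0.64, and 0.64 / 1.64 = 0.39. The significance rates are from simulation.

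| d (SD) | pooled r, 6 MMT 0 | p<0.05 | pooled r, 16 MMT 0 | p<0.05 |
|---|---|---|---|---|
| 1 | 0.14 | 12% | 0.20 | 19% |
| 1.5 | 0.26 | 31% | 0.36 | 54% |
| 2 | 0.39 | 62% | 0.50 | 88% |

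Adjusting for MMT group returns the rate to about 5% in every row. A test within the MMT 0 patients alone also stays at about 5%.

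**4. Precision in the MMT 0 group.** Fisher z interval: tanh(atanh(r) ± 1.96/√(n−3)). For an observed r of 0.5, atanh(0.5) = 0.549.

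- n = 16: 0.549 ± 0.544, giving 0.01 to 0.80.
- n = 6: 0.549 ± 1.132, giving -0.52 to 0.93.

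Power for a true r of 0.5 is about 51% with 16 patients and 16% with 6. About 30 MMT 0 patients would be needed for 80% power. The documents give no coefficient for the modest or moderate correlations they cite, so r = 0.5 is illustrative.

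**The case against.** **No correlation is planned, so the rates in the table describe no planned test.** This stands. They show what a natural addition would do. The more basic fault is that no association analysis exists, and the fix has to start there.

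**The stated target is acute stroke patients generally.** This also stands. The question, objective and H1 are broad, and Problem Statement describes the gap as limited study in adult acute stroke patients. A reader might infer that MMT 0 patients are the one gap the protocol sets out to fill, or that broad enrolment is an error. The documents support neither. Under H1 as written, an association across the severity range is not false; it is unadjusted for initial severity.

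**sEMG may add information above MMT 0.** A reader might infer from Table 1, where grade 1 already means "Evidence of slight contractility, with no joint motion", that sEMG merely repeats the examination from that grade upward. Table 1 shows only that contraction is clinically detectable. The same section says MMT grades joint motion rather than individual muscles, whereas sEMG gives rate, duration and amplitude per muscle. The documents do not say whether correlations were looked for above MMT 0. An interaction term leaves the matter open.

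**The gap is assumed.** Correct. At 1 SD the effect is modest, though still above 5%.

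**The subgroup is small and loosely defined.** Correct. The examination form has one MMT score per visit while five movements are tested, so MMT 0 is undefined for a patient with mixed grades. Five muscles by three parameters gives 15 sEMG measures, and splitting them without a stated priority multiplies tests. The answer is a definition and an exploratory label.

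**Conclusion.** The point holds in this form: the planned tests cannot show prediction, and the plan has no baseline MMT term or split to stop initial severity from producing an apparent one. That MMT 0 recordings involve passive movement while the others are active is a reason, in the documents themselves, to show sEMG values separately.

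The size is conditional. It rests on an unplanned pooled correlation, an assumed 6 to 16 MMT 0 patients, an equal assumed gap of 1 to 2 SD on both variables, and no association within groups. A reader might take the upper rates as the plan's own false-positive rate. They are not, because no planned test uses the between-group contrast in that way. Nor do the documents show that sEMG fails to predict in either group.

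**What to change.** - **Data Analysis.** Add a regression of 3-month FMA-UE on day-3 sEMG that includes day-3 MMT group (0 versus ≥1). Define the group for patients whose movements differ in grade, and name in advance which sEMG measures the model uses.
- **Table 2.** Show sEMG results and the number of patients by day-3 MMT group, because the recording conditions differ.
- **Exploratory.** Report the sEMG-by-MMT-group interaction and the MMT 0 estimate with its 95% CI, labelled exploratory.
- **Interpretation.** State that no claim that sEMG predicts where clinical examination cannot will rest on a pooled, unadjusted result.

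Cost: the predictive model has to be written, since none exists, and Table 2 gains a split. MMT, FMA-UE and sEMG are already scheduled at every visit, so no new data are needed and enrolment is unchanged. The downside is a wide MMT 0 interval, which is the precision that 30 patients can give.
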